7 DERIVED AND COMPUTED VARIABLES

Mean change from baseline is the mean of all individual subjects' change from baseline values (baseline is defined in Section 11.1.4 "Definitions for Statistical Data Analysis"). Each individual change from baseline will be calculated by subtracting the individual subject's baseline value from the value at the timepoint. The individual subject's change from baseline values will be used to calculate the mean change from baseline.

Reported BMI will be calculated from the body weight and height using the following formula:

As part of the PMI Quality Control (QC) activity, data listings will be reviewed by Covance and PMI before database lock, with no access to the randomization sequence information. Full details will be available in the data review plan.

Philip Morris Products S.A.

Statistical Analysis Plan

Confidential

Protocol ZRHR-PK-02-JP

Final v 2.0 / 07 April 2014

Page 18 of 73

$$BMI = \frac{\text{weight in kilograms}}{\text{height in meters}^2} \quad (\text{kg/m}^2)$$

The QT interval corrected using Fridericia's formula (QTcF) will be calculated as follows:

$$QTcF = \frac{QT}{\sqrt[3]{60/HR}}$$

The QT interval corrected using Bazett's formula (QTcB) will be calculated as follows:

$$QTcB = \frac{QT}{\sqrt[2]{60/HR}}$$

The geometric coefficient of variation (CV) will be calculated using the following formula:

$$CV = 100\sqrt{e^{\text{var}}-1}$$

where var = the variance from the log transformed data.

7.1 Pharmacokinetic Parameters

The following PK parameters will be determined from the plasma concentration-time profiles of nicotine using non-compartmental procedures in WinNonlin Phoenix, Version 6.2.1, or higher:

Statistical Analysis Plan Final v 2.0 / 07 April 2014 Confidential
Page 19 of 73

Table 3: Definition of PK Parameters

Parameter	Definition
AUC _(0-last)	Area under the plasma concentration-time curve from start of product use to the time of the last quantifiable concentration.
AUC _(0-t')	Area under the plasma concentration-time curve from start of product use to the subject-specific time (t') of maximum nicotine concentration following single use of the CC or NRT gum product, between the THS 2.2 and CC, as well as the THS 2.2 and NRT gum.
AUC _(0-∞) %AUC _{extrap}	Area under the plasma concentration-time curve from start of product use extrapolated to infinite time.
%AUC _{extrap}	Percentage of AUC that is extrapolated from t _{last} to infinity.
C _{max}	Maximum observed plasma concentration.
C _{last}	Last quantifiable concentration.
t _{last}	Time of the last quantifiable concentration.
t _{max}	Time of maximum observed plasma concentration.
λ_z	Terminal elimination rate constant, estimated by linear regression analysis of the natural log-transformed concentration-time data.
t _{1/2}	Terminal elimination half-life.

Additional PK parameters may be determined in order to support the interpretation where appropriate.

The actual blood sampling times post-exposure collected in the eCRF will be used in the computation of the PK parameters, with the exception of pre-exposure (-15 mins) blood sampling time which will be considered as time zero (T_0) .

7.1.1 Calculation of C_{max} and t_{max}

The minimum requirement for the determination of the C_{max} is the inclusion of at least one quantifiable concentration within 1 hour post-exposure.

 C_{max} and t_{max} will be obtained directly from the plasma concentration-time profiles. If C_{max} occurs at more than one time point, t_{max} will be assigned to the first occurrence of the C_{max} .

7.1.2 Calculation of AUC

The minimum requirement for the calculation of the AUC is the inclusion of at least 3 consecutive plasma concentrations above the lower limit of quantification (LLOQ), with at least 1 of these concentrations following C_{max} .

AUC_(0-last) and AUC_(0-t') will be calculated using the linear trapezoidal method.

AUC_(0-t') will be calculated automatically by linear interpolation within WinNonlin, where t' is the subject-specific actual time of maximum nicotine concentration following single

Statistical Analysis Plan Final v 2.0 / 07 April 2014 Confidential

Page 20 of 73

use of the CC or NRT gum product, between the THS 2.2 and CC, as well as the THS 2.2 and NRT gum.

 $AUC_{(0-\infty)}$ will be calculated as follows:

$$AUC_{0-\infty} = AUC_{0-last} + \left(\frac{C_{last}}{\lambda_z}\right)$$

Where C_{last} is the last quantifiable concentration and λ_z is the terminal elimination rate constant.

%AUC_{extrap}, the percentage of AUC_(0- ∞) extrapolated beyond t_{last} , will be calculated according to the following formula:

$$\%AUC_{extrap} = \left(1 - \frac{AUC_{0-last}}{AUC_{0-\infty}}\right) \times 100$$

 $AUC_{(0-\infty)}$ values where the percentage extrapolation is greater than 20% will be flagged in the data listings and will be reviewed for inclusion in the analysis during the ore-analysis data review.

7.1.3 Criteria for Calculating the Apparent Terminal Elimination Half-Life

 $t_{1/2}$ will be calculated according to the following formula:

$$t_{1/2} = \frac{\ln(2)}{\lambda_2}$$

where λ_z will be calculated by least squares (LS) linear regression of the terminal portion of the log-transformed plasma concentration-time curve.

The start of the terminal elimination phase for each subject will be defined by visual inspection and will be the first point at which there is no systematic deviation from the log-linear decline in plasma concentrations. The concentrations included in the terminal elimination phase will be flagged in the data listings.

Period of Estimation

 Apparent terminal (elimination) half-lives will be calculated, where possible, over at least 2 half-lives. Where an apparent terminal half-life is estimated over less than 2 half-lives, it will be flagged in the data listings.

Statistical Analysis Plan Final v 2.0 / 07 April 2014 Confidential
Page 21 of 73

11 1010 11 11

 An apparent terminal half-life will not be reported if it can only be calculated over a period that is less than 1.5 half-lives.

Number of Data Points

 At least 3 data points with nicotine concentration greater than the LLOQ will be used for each subject in the regression analysis. An apparent terminal half-life will not be reported if derived from less than 3 data points.

Goodness of Fit

- When assessing apparent terminal phases, the coefficient of determination, R² adjusted value, will be used as a measure of the goodness of fit of the data points to the determined line. This parameter will be used as it is considered to be a better assessment of the goodness of fit, compared to R², as it adjusts for the number of points included in the line therefore allowing for a more direct comparison between elimination phases determined using different numbers of data points.
- Apparent terminal half-life will only be calculated if the R² adjusted value of the regression line is greater than or equal to 0.7.

7.1.4 Anomalous Values

If a concentration value is considered to be anomalous due to being inconsistent with the expected PK profile it will be flagged in the listings and will be reviewed for inclusion in the analysis during the pre-analysis data review.

7.2 Biomarkers

7.2.1 CYP2A6

CYP2A6 activity is calculated in plasma as the metabolic ratio of trans-3' hydroxycotinine and cotinine, both expressed in molar equivalent (nmol/L) (**Jacob et al, 2011**):

$$CYP2A6 = \frac{HCOT[ng/mL] \times 5.202}{COT[ng/mL] \times 5.675}.$$

Any values below the LLOQ or above the upper limit of quantification (ULOQ) in the component parameters will not be imputed and the derived variable will be set to missing.

The conversion factor will be applied as follows:

Cotinine The molecular weight is 176.2178 g/mol (Chemical Information (COT) Specialized Information Services RN:486-56-6) Therefore to

Specialized Information Services RN:486-56-6) Therefore to transform COT from ng/mL to nmol/L, the result in ng/mL will be multiplied by 5.675

Statistical Analysis Plan Final v 2.0 / 07 April 2014

Page 22 of 73

Confidential

Trans-3'hydroxycotine (HCOT) The molecular weight is 192.217 g/mol (Chemical Information Specialized Information Services RN:34834-67-8) Therefore to transform HCOT from ng/mL to nmol/L, the result in ng/mL is

multiplied by 5.202

The converted results will be reported to three decimal places and the ratio will be reported as a percentage to two decimal places.

7.3 Questionnaires

7.3.1 Fagerström Test for Nicotine Dependence

The FTND will be used in its revised version (**Heatherton et al, 1991**). These questions are to be answered by the subject themselves. It is conducted at Screening only to determine subject's dependence on nicotine.

Table 4 describes the six questions the questionnaire consists of, and the scores associated with each question.

The FTND total score will be derived by summing the individual item scores if all items are non-missing, otherwise the total score will be set to missing.

For the FTND total score, descriptive statistics and frequency tables according to the following classification will be provided (Fagerström et al, 2012):

- Mild 0 − 3
- Moderate 4 6
- Severe 7 − 10

Statistical Analysis Plan Final v 2.0 / 07 April 2014 Confidential

Page 23 of 73

Table 4: Scoring for the Fagerstrom Test for Nicotine Dependence

	FTND Question	Response	Score
1	How soon after you wake up do you smoke your first cigarette?	 Within 5 minutes 6 to 30 minutes 31 to 60 minutes After 60 minutes 	3 2 1 0
2	Do you find it difficult to refrain from smoking in places where it is forbidden?	YesNo	1
3	Which cigarette would you hate most to give up?	The first one in the morningAny other	1
4	How many cigarettes per day do you typically smoke?	 10 or less (up to ½ pack) 11 to 20 (a little more than ½ pack, up to a full pack) 21 to 30 (a little more than a pack, up to 11/2 packs) 	0 1 2
		up to 1½ packs) 31 or more (more than 1½ packs)	3
5	Do you smoke more frequently during the first hours after waking than during the rest of the day?	YesNo	1 0
6	Do you smoke if you are so ill that you are in bed most of the day?	YesNo	1

7.3.2 Questionnaire of Smoking Urges Brief

The QSU-brief (Cox et al, 2001). is a self-reported questionnaire completed 10 times at the following timepoints at Day 1 and Day 3:

- The first assessment will be done 15 min prior to T₀
- The subsequent 9 assessments will be done as follows:
 - o For subjects on THS 2.2 or CC, assessments will be done at: T_0+15 min, T_0+30 min, T_0+45 min, T_0+1 hr, T_0+2 hr, T_0+4 hr, T_0+6 hr, T_0+9 hr, T_0+12 hr (with an allowed time window of +10 min each).
 - o For subjects on NRT gum, assessments will be done at: T_0+20 min, T_0+30 min, T_0+45 min, T_0+1 hr, T_0+2 hr, T_0+4 hr, T_0+6 hr, T_0+9 hr, T_0+12 hr (with an allowed time window of +10 min each).

The QSU-brief consists of 10 items as presented in Table 5.

Statistical Analysis Plan Final v 2.0 / 07 April 2014 Confidential

Page 24 of 73

Table 5: Questionnaire of Smoking Urges Brief - Questions and Factors

8	Question	Factor
1	I have a desire for a cigarette right now	1
2	Nothing would be better than smoking a cigarette right now	2
3	If it were possible, I probably would smoke now	1
4	I could control things better right now if I could smoke	2
5	All I want right now is a cigarette	2
6	I have an urge for a cigarette	1
7	A cigarette would taste good now	1
8	I would do almost anything for a cigarette now	2
9	Smoking would make me less depressed	2
10	I am going to smoke as soon as possible	1

All items will be rated on a 7-point scale, ranging from 1 (strongly disagree) to 7 (strongly agree). Higher scores indicate a higher urge to smoke.

Two factor scores and a total score will be derived (Cox et al, 2001). Each factor is a subset that includes 5 of the 10 questions as defined in Table 5. Factor 1 represents the desire and intention to smoke with smoking perceived as rewarding, while Factor 2 represents an anticipation of relief from negative effect with an urgent desire to smoke.

The factors and total scores will be calculated by averaging non-missing item scores if at least 50% are non-missing, otherwise the factor or total score will be set to missing.

7.3.3 **Modified Cigarette Evaluation Questionnaire**

The MCEQ (Cappelleri et al, 2007) will be completed by the subject him/herself at Day 1 and Day 3, during CC and THS 2.2 (product use only) to assess the degree to which subjects experience the reinforcing effects of smoking.

Statistical Analysis Plan Final v 2.0 / 07 April 2014 Confidential
Page 25 of 73

The MCEQ consists of 12 items as presented in Table 6.

Table 6: Modified Cigarette Evaluation Questionnaire - Questions and Subscales

	Question	Subscale
1	Was smoking satisfying?	Smoking Satisfaction
2	Did cigarettes taste good?	Smoking Satisfaction
3	Did you enjoy the sensation in your throat and chest?	Enjoyment of Respiratory Tract Sensations
4	Did smoking calm you down?	Psychological Reward
5	Did smoking make you feel more aware?	Psychological Reward
6	Did smoking make you feel less irritable?	Psychological Reward
7	Did smoking help you concentrate?	Psychological Reward
8	Did smoking reduce your hunger for food?	Psychological Reward
9	Did smoking make you dizzy?	Aversion
10	Did smoking make you nauseous?	Aversion
11	Did smoking immediately relieve your craving for a cigarette?	Craving Reduction
12	Did you enjoy smoking?	Smoking Satisfaction

Items are assessed on a 7-point scale, ranging from 1 (not at all) to 7 (extremely). Higher scores indicate greater intensity on that scale.

The subscales scores will be derived by averaging the individual non-missing item scores if at least 50% are non-missing, otherwise the subscale score will be set to missing.

7.3.4 Cough Assessment

Subjects will be asked if they have experienced a regular need to cough (e.g., coughing several times) in the last 24 hours prior to assessment. If the answer is 'yes', they will be asked to complete a visual analogue scale (VAS), three Likert scale questions and an open question assessing their cough during previous 24 hours. Assessments will be done on a daily basis from Day 0 to Day 4.

The VAS will assess how bothersome cough is to the subject ranging from 'not bothering me at all' to 'extremely bothersome', and this will be given a numeric value between 0 and 100.

Statistical Analysis Plan Final v 2.0 / 07 April 2014

Page 26 of 73

Confidential

Subjects will also be asked to assess the intensity and frequency of cough and the amount of sputum production on Likert scales as presented in Table 7

Table 7: Cough Assessment Likert Scales

	Question	Likert Scale
1	The intensity of cough	1 = very mild
	2 =2	2 = mild
		3 = moderate
		4 = severe
		5 = very severe
2	The frequency of cough	1 = rarely
		2 = sometimes
		3 = fairly often
		4 = often
		5 = almost always
3	The amount of sputum production	0 = no sputum
	•	1 = a moderate amount of sputum;
		2 = a larger amount of sputum;
		3 = a very large amount of sputum.

7.4 Categorical Variables

Table 8: Categorical Variable Definitions

Variable	Categories	
BMI (kg/m ²)	Underweight:	< 18.5 ¹
	Normal range:	≥ 18.5 and < 25.0
	Overweight:	≥ 25.0 and < 30.0
	Obese:	≥ 30.0
FTND total score	Mild:	0 - 3
	Moderate:	4 - 6
	Severe:	7 - 10
ISO nicotine level (mg)	≤ 0.6	
	$> 0.6 \text{ to} \le 1.0$	
	> 1.0 ¹	
ISO tar yields (mg)	1-5	
	6-8	
	9-10	
	>10 ¹	
Daily CC consumption (cig/day)	<10 ¹	
	10-19	
	>19	
NRT Use	< 10 min	
	\geq 10 min and \leq 30 r	nin
	35±5 min	
	>40 min	
CO breath test level (ppm)	≤ 10	
M. 1. 7	> 10	

Statistical Analysis Plan Final v 2.0 / 07 April 2014 Confidential
Page 27 of 73

Table 8: Categorical Variable Definitions

Variable	Categories
COHb level	≤ 2%
	> 2%
Adverse event severity	Mild
500 c. patrio de minor tubrico — di minorección person manor en de cultura de Pet	Moderate
	Severe
Adverse event relationship	Related
	Not related
Adverse event expectedness	No
	Yes
Action taken due to adverse event	Discontinuation from study
	Related to product use (if any of the
	following applies: interrupted, stopped,
	or reduced)
	Treatment given (yes/no)
	Other action taken
Outcome of adverse event	Death related to adverse event
	Not recovered or not resolved
	Recovered or resolved
	Recovered or resolved with sequelae
	Recovering or resolving
	Unknown
Seriousness Criteria	Fatal
ochoushess officha	Life-threatening
	Requires hospitalization
	Results in disability/incapacity
	Congenital anomaly/birth defect
Severity of device event	Major
Severity of device event	Minor
	IVIII IOI

Note that due to inclusion criteria for the study there should not be any subjects underweight, or reporting <10 cig/day, or with ISO nicotine level > 1.0 mg, or ISO tar yields > 10mg; therefore these categories will not be presented unless there is at least one response.

8 SAMPLE SIZE JUSTIFICATION

A total of 62 subjects will be randomized. This sample size is the sum of the sample size requirements for the THS 2.2:CC comparison and the THS 2.2:NRT gum comparison (as described in detail below).

The estimates for the within-subject CV for nicotine C_{max} (36%) and AUC_(0-last) (21%) are based on the data collected in the ZRHX-PK-02 clinical study (**ZRHX-PK-02**, **2012**) comparing the nicotine PK profiles of Tobacco Heating System 2.1, the predecessor of THS 2.2 (regular tobacco stick) and CC. In the absence of data comparing THS and NRT gum, the same CVs were assumed for the calculation of the sample size related to the THS 2.2:NRT gum comparison.

Statistical Analysis Plan Final v 2.0 / 07 April 2014 Confidential
Page 28 of 73

Anticipated mean C_{max} and AUC_(0-last) for THS 2.2 and CC were based on data from the ZRHX-PK-02 study (**ZRHX-PK-02**, **2012**). Anticipated mean C_{max} and AUC_(0-last) for NRT gum were based on data reported by **Dautzenberg et al.**, **2007**.

The sample sizes of this study assume a drop-out rate no larger than 10%.

Sample size calculations were conducted using SAS^{\otimes} version 9.2 for the 95% CI of the mean differences between paired observations (proc power onesamplemeans) in the natural log scale (Senn, 2002). The SAS^{\otimes} implementation of the method published by Beal, 1989 was adopted to estimate the probability of obtaining at most the target 95% CI of $\pm 20\%$.

A total of 44 subjects are needed to estimate the geometrical mean C_{max} ratio between THS 2.2 and CC with a 90% probability of obtaining a margin of error (95% CI) of at most $\pm 20\%$, assuming that THS 2.2 have a nicotine C_{max} similar to CC (geometrical mean ratio equal to 1.00). This sample size is sufficient to provide 90% probability of obtaining a margin of error of at most $\pm 20\%$ for the geometrical mean AUC_(0-last) ratio between THS 2.2 and CC, assuming a similar extent of nicotine absorption for the 2 products (ratio equal to 1.00).

A total of 18 subjects are needed to estimate the geometrical mean $AUC_{(0-last)}$ ratio between THS 2.2 and NRT gum with a precision allowing for the lower bound of the 95% CI exceeding 1.00, with 90% power, assuming a ratio of 1.28 between the geometrical mean of THS 2.2 and NRT gum. This sample size is sufficient to provide 90% power of obtaining a lower bound of the 95% CI of the geometrical mean C_{max} ratio between THS 2.2 and NRT gum, exceeding 1.00, assuming a geometrical mean ratio between THS 2.2 and NRT gum of 2.00.

9 CHANGES FROM THE PROTOCOL SPECIFIED STATISTICAL ANALYSIS

Safety analyses will not be performed by product. Due to the study design it was determined that this presentation is not clear because of the product test at Admission and the selection of arbitrary time points for defining periods associated to the different study products may be misleading. In addition, the safety laboratory evaluations will only be collected prior to any product use and following the use of both products.

Shift tables for safety endpoints will not be produced for this study, because the relevant information will be provided in listings.

Statistical analysis for blood COHb (%) and exhaled CO (ppm) measurements and the QSU-brief questionnaire data will be performed including interaction terms for product and time point to enable LS means to be calculated at each time point in order to explore the pattern of the THS 2.2 effect over time. The main comparison between products will be the comparison over all time points.

Statistical Analysis Plan Final v 2.0 / 07 April 2014 Confidential
Page 29 of 73

Spirometry predicted values will not be standardized to the NHANES III predicted set as planned in the protocol. Predicted FEV₁ and FVC will be calculated according to the formula recommended by the Japanese Respiratory Society (Sasaki H, Nakamura M et al., 2001) for Japanese population.

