Confidentiality statement: Data and information contained in this document are considered to constitute trade secrets and confidential commercial information, and the legal protections provided to such trade secrets and confidential information are hereby claimed under the provisions of applicable law. No part of this document may be publicly disclosed without the written consent of Philip Morris Products S.A.

Philip Morris Products S.A.	Clinical Study Protocol	Confidential
ZRHR-PK-02-JP	Final 1.0 / 21 June 2013	Page 8 of 122

urge-to-smoke (QSU-brief), including the assessment time points as repeated measurements. The results will be presented in terms of least square means and 95% CI for the THS 2.2 -CC and THS 2.2 -NRT gum differences.

Safety: The safety population will comprise all subjects who are exposed to THS 2.2 during the study, including the THS 2.2 test at admission.

Adverse event data will serve as the primary assessment of safety. All safety data will be listed and tabulated by sequence and by product use.

Sample Size:

A total of 62 subjects will be randomized. This sample size is the sum of the sample size requirements for the THS 2.2:CC comparison and the THS 2.2:NRT gum comparison (as described in detail below).

The anticipated within-subject coefficients of variation for nicotine C_{max} and $AUC_{(0-last)}$ are 36% and 21%, respectively.

The sample sizes of this study assume a drop-out rate no larger than 10%.

THS 2.2 :CC comparison

A total of 44 subjects are needed to estimate the mean C_{max} parameter ratio between THS 2.2 and CC with a 90% probability of obtaining a margin of error (95% CI) of at most ±20%, assuming that THS 2.2 have a nicotine C_{max} similar to CC (ratio equal to 1.00). This sample size is sufficient to provide 90% probability of obtaining a margin of error of at most ±20% for the AUC_(0-last) ratio between THS 2.2 and CC, assuming a similar extent of nicotine absorption for the 2 products (ratio equal to 1.00).

THS 2.2 :NRT gum comparison

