4.2 Rationale for Study Design and Control Group(s)

The minimum age of 23 years age in the inclusion criteria was selected based on:

- The legal age of smoking in Japan is 20 years.
- To account for the 3 years of smoking history.

In this study, CCs (up to 1.0 mg nicotine ISO yield/CC) will be used as a reference product and a market-approved pharmaceutical NRT gum 2 mg (Nicorette[®]) will be used as non-investigational reference point. The NRT gum has been selected as the reference point, because of its availability over the market. The NRT gum will serve as a reference point for comparison with THS 2.2 for the following endpoints:

- Nicotine PK parameters.
- Urge-to-smoke.
- Safety profile.

The nicotine wash-out period was set to at least 24 hours (>5 x elimination $t_{1/2}$) as the elimination $t_{1/2}$ of nicotine in blood is around 2 hours in Caucasian smokers (Benowitz et al., 2009).

The use of estrogen contraceptive is known to accelerate nicotine clearance by 20% to 30% in women as compared to women who do not take such contraceptives (Benowitz et al., 2006). Therefore, for the purpose of this study, it is not allowed to use hormonal contraception containing estrogens. This also applies to hormone replacement therapy.

In this study, THS 2.2 will be tested against CC and NRT gum will be used as a reference point product.

Furthermore, CYP2A6 activity will be assessed in this study. Asians on average metabolize nicotine more slowly than Caucasians do, at least in part due to a high prevalence of the CYP2A6 alleles associated with reduced or absent enzyme activity (Matta et al., 2006).

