12.1.1 Stratification Criteria

For analysis, the following stratification criteria will be used:

- Sex (male and female)
- CC nicotine level at Admission (ISO nicotine levels ≤ 0.6 mg and 0.6 to 1 mg)

In addition, for the safety data, the analysis will be stratified by sequence and by study periods (Screening, product test, product exposure, and safety follow-up period).

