12.6.5 Safety Endpoints

In general, all safety data will be listed and tabulated on the safety population by sequence, using the approach described in Section 12.1.3. Safety variables collected during exposure periods will also be reported by product exposure.

AE data will serve as the primary assessment of safety. Other safety variables monitored in this study include: respiratory symptoms (cough assessment, VAS, and Likert scales); vital signs (systolic and diastolic blood pressure, pulse rate, respiratory rate); spirometry; ECG data; clinical chemistry, hematology, and urine analysis safety panel; physical examination; and concomitant medications.

The number and percentage of subjects with AEs and SAEs will be tabulated by system organ class and preferred term. Summaries will also be presented for AEs leading to withdrawal, AEs leading to Death, AEs by relatedness to product exposure, AEs by severity, and laboratory AEs. Tabulations will be performed for both the number of subjects experiencing an event and the number of events. The number and percentage of device events and of subjects with device events will be tabulated by sequence.

The number and percentage of subjects with clinical findings will be tabulated by sequence for laboratory parameters. Shift tables showing change from baseline of clinical findings will be provided for: ECGs, physical examinations, and laboratory parameters (both shifts in

Confidentiality statement: Data and information contained in this document are considered to constitute trade secrets and confidential commercial information, and the legal protections provided to such trade secrets and confidential information are hereby claimed under the provisions of applicable law. No part of this document may be publicly disclosed without the written consent of Philip Morris Products S.A.

Philip Morris Products S.A.	Clinical Study Protocol	Confidential
ZRHR-PK-02-JP	Final 1.0 / 21 June 2013	Page 96 of 122

normal ranges and toxicity grades). Descriptive statistics will be summarized by visit and change from baseline for laboratory parameters, ECG, respiratory symptoms, and vital signs.

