6.1.1 Timing of Confinement Period

The 6 day confinement period consists of:

- The Admission Day from admission on site until 06:30 AM on Day 0.
- The first washout period: from 06:30 AM on Day 0 until the time of first product use (T₀) in the time window 6:00 AM-9:00 AM of Day 1.
- The first product exposure period (1 day): starting from T₀ on Day 1, ending 24 hours after T₀.
- The second washout period: from the end of the first product exposure (24 hours after T₀ on Day 1) on Day 2 until the time of product use in the time window 6:00 AM-9:00 AM on Day 3.
- The second product exposure period (1 day): starting from T₀ on Day 3, ending 24 hours after T₀.
- The discharge procedures from 24 hours after T₀ of the second product use until the time of discharge on Day 4.

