11.6.4.1 Safety Reporting

An exposure emergent AE is defined as an AE that occurs after first product use or that is present prior to first product use and becomes more severe after first product use. All other AEs will not be summarized but provided in listings only.

All AEs occurring from the signing of informed consent will be recorded electronically. The AE listings will include all AEs captured in the database at any time during the study (including those from subjects who were not in the safety population). All AEs occurred after the product test of THS 2.2 or NRT gum will be included in the summary tables. During the screening period prior to the first THS 2.2 or NRT gum product use, only study procedure related AEs will be included in the summary tables.

AEs reported from subjects that have a first product use, but were not randomized will be summarized in a separate sequence: "Exposed but not randomized". The remainder of safety endpoints assessed in enrolled subjects that have a first product use, but were not randomized will be summarized in a separate sequence: "Enrolled but not randomized".

Partial dates will not be imputed, but assumptions will be made as follows to assign to exposure-emergent or not:

Date information	Assign as	
Partial date, e.g.,May2012, or2011. If month/year is the same as, or later than the month and/or year of		
Screening. Partial date, e.g.,May2012, or2011. If month and/or year is earlier than the month and/or year of Screening.		

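### AE tables split only by sequence cannot separate THS 2.2 from CC, and SAP 9 does not account for the protocol's study-period strata

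*SAP*

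**What the plan says.** Protocol commitments:

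- Synopsis, Statistical Methods: "All safety data will be listed and tabulated by sequence and by product use". The synopsis and 12.6.5 both make AE data the primary safety assessment.
- Section 12.6.5: "Safety variables collected during exposure periods will also be reported by product exposure".
- Section 12.1.1, for safety data: "the analysis will be stratified by sequence and by study periods (Screening, product test, product exposure, and safety follow-up period").
- Section 4.2: "The NRT gum will serve as a reference point for comparison with THS 2.2 for the following endpoints". Safety profile is on the list that follows.

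SAP provisions:

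- Section 9: "Safety analyses will not be performed by product". It gives three reasons: the product test at Admission, the worry that "the selection of arbitrary time points for defining periods associated to the different study products may be misleading", and safety laboratory sampling only before any product and after both. It does not mention the study-period strata.
- Section 6.1.1: "The first product exposure period (1 day): starting from" T0 on Day 1 and ending 24 hours later. A matching period is defined on Day 3, with the wash-outs and the discharge interval defined separately.
- Section 11.6.4.1: "All AEs occurred after the product test of THS 2.2 or NRT gum will be included in the summary tables". Before first product use, only procedure-related AEs are counted.
- Sections 11.1.3 and 11.6.4.2: AE tables are by sequence and overall, then by system organ class (SOC) and preferred term (PT), severity, relatedness, action taken and similar. Relatedness has two product categories, THS 2.2/CC and NRT gum (general AE table and Table 15.2.6.3).

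**The concern.** In a crossover every sequence receives both of its products, so a sequence column does not show which product preceded an event. The planned AE tables also run from the Day -1 product test to the end of follow-up. All subjects try THS 2.2 and then gum at that test, may smoke their own cigarettes until 11 PM that day, and smoke freely after discharge. Without a product or period split, the tables pool these exposures with the two single-use days.

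What is at stake is the descriptive safety statement about THS 2.2 against CC, which the protocol said would be available. The AE listing will carry onset times, but the SAP has no rule assigning an AE to a product or period. A rule chosen after sequences are unblinded would be post hoc, and two analysts could count differently.

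**Working it through.** The plan gives no figure to reproduce. The check compares texts, followed by simple counting.

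**1. Do SAP 9's reasons apply to AEs?**

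- *Arbitrary time points.* SAP 6.1.1 already sets the windows at T0 to T0+24 h on Day 1 and Day 3. SAP 10 defines actual product exposure on those days from recorded use times, and protocol 8.2.1 records AE start dates and times. An onset inside a window can be assigned without a new choice of time point.
- *Product test at Admission.* Protocol 12.1.1 makes the product test its own stratum. Keeping that stratum would answer the objection.
- *Laboratory timing.* This is valid for laboratory data. It does not apply to AEs, which are recorded continuously.

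**2. What can each planned AE output separate?**

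| Contrast | By sequence | By relatedness (Table 15.2.6.3) |
|---|---|---|
| THS 2.2 vs CC, sequences 1 and 2 | No | No: one pooled category |
| THS 2.2 vs gum, sequences 3 and 4 | No | Largely: no CC is assigned there, though own cigarettes are smoked on Day -1 and in follow-up |
| Day -1 THS 2.2 test vs single use, either group | No | No |
| Day -1 gum test vs single use, Group-2 | No | No |

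Group-1 uses gum only at the Day -1 test, so gum-related events there can be placed by inference.

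**3. Other safety data.** ECG and vital signs are summarised by sequence and day. Cough is too, with assessments 24 hours after each T0. Product can be read from sequence and day for all three, so the gap is specific to AEs.

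**4. Illustration (assumed counts).** Suppose 6 of the 44 Group-1 subjects have an AE judged related to THS 2.2/CC, 3 in each sequence. The planned columns show 3/22 = 13.6% and 3/22 = 13.6%, and together 6/44 = 13.6%. The same output fits each of these:

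- all 6 after THS 2.2 single use: 6/44 - 0/44 = +13.6 points;
- 3 after each product: 3/44 - 3/44 = 0;
- all 6 after CC: 0/44 - 6/44 = -13.6 points;
- all 6 at the Day -1 product test: no event in either exposure period.

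For m affected subjects the unresolved range is ±m/44. That is ±4.5 points for m = 2 and ±22.7 for m = 10.

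**5. Planned denominators for a split.** THS 2.2: 22 + 22 = 44 in Group-1 and 9 + 9 = 18 in Group-2, total 62. CC: 22 + 22 = 44. Gum: 9 + 9 = 18. The sum is 62 + 44 + 18 = 124 = 62 × 2 product days.

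**The case against.** The strongest case for the SAP has four parts.

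- **The by-product change is disclosed and reasoned.** This stands. A reader might infer that the whole change was left unstated, but SAP 9 states it and says why. Only the loss of the period strata goes unmentioned there. Protocol 12.1 would still let the study report record it.
- **Relatedness already gives a product breakdown.** This stands in part. A reader might infer that no AE output distinguishes any product. That is wrong: Table 15.2.6.3 counts gum-related events apart from THS 2.2/CC-related ones, which largely serves the gum comparison named in protocol 4.2. It does not help THS 2.2 against CC.
- **The 6.1.1 windows set study timing and do not attribute AEs.** This also stands in part. Subjects abstain after a single use, and protocol 2.3.3 lists withdrawal symptoms as a foreseeable risk. An event 20 hours after T0 may therefore be withdrawal, and a late product effect may start in wash-out. Windowing by onset needs that caveat. It remains a pre-specified and reproducible description, which pooling across sequences does not provide.
- **Safety is a monitoring objective in a single-use PK study, and nothing is lost.** Onset times are recorded, and SAP 12.4 allows labelled additional analyses. This limits the severity. It does not explain leaving out a tabulation the protocol promised, and a rule set before unblinding is better than one set later.

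**Conclusion.** The point holds in a limited form. The protocol called for AEs by product exposure and by study period; the SAP delivers neither. It gives reasons for the first omission that are weak for AEs, and it does not mention the second. The main loss is that no planned AE table separates THS 2.2 from CC in the 44 Group-1 subjects. The Day -1 test is also not separated from single use.

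A reader might infer a definite amount of hidden safety difference. The documents do not support that: they give no AE rate, and the 6-of-44 example is an assumption chosen to show the arithmetic. AE reporting is descriptive, so no test result is at issue. The primary PK analysis is unaffected, and vital signs, ECG and cough can be read by sequence and day. The change is worth making because it is cheap and restores a protocol commitment.

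**What to change.** In SAP 11.6.4.2 add one descriptive Safety-population table of AEs by SOC and PT, assigned by onset date and time. Keep the by-sequence tables. Columns:

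1. Screening: procedure-related events before the first product test only.
2. Product test: from the first product test to 06:30 AM on Day 0, with exposed-but-not-randomized subjects in the denominator. This column isolates no product; it keeps these events out of the exposure columns.
3. Exposure, T0 to T0+24 h, shown by group: THS 2.2 (planned N = 44 in Group-1, 18 in Group-2), CC (44), NRT gum (18).
4. Wash-out.
5. From T0+24 h on Day 3 through discharge and follow-up.

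Footnote that assignment is by onset time and not cause, so withdrawal symptoms or late effects may fall in another column. Split the pooled THS 2.2/CC relatedness category only if the eCRF records the two separately.

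In SAP 9, state that the by-product change does not apply to AEs, and say how the protocol 12.1.1 study-period strata are handled.

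Cost: one table shell with its program and a few sentences in SAP 9. The protocol already requires AE start times to be recorded, so no site procedure changes. The downside is that some readers may take onset timing as attribution, which the footnote addresses.
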